## 3C.7. Outcome Measures

**3C.7.1. Measure of Primary Outcome Variable: IID Lockout Events.** The primary outcome

measure will be frequency of IID lockout events from baseline to 9-month follow-up post-randomization, collected from the Santa Fe DWI program database for each first-time DWI offender participant. Marques, Voas and colleagues have demonstrated in a series of investigations that frequency of lockout events strongly predicts DWI recidivism over time, and as such, IID lockout events are an important and useful proxy measure for DWI recidivism. Given the length of time necessary to accumulate DWI recidivism data (average length of time varies across locales and can be between 2 and 8 years), IID lockout events provide a direct and accessible measure of DWI recidivism within the two-year project timeline.

**3C.7.2. Measures of Secondary Outcome Variables and Mediators.** Alcohol use by the DWI offender, a secondary outcome, will be assessed at baseline, 3-month follow-up, and 9-month follow-up with versions of the Form 90 adapted for online assessment for the CFMs (Form 90-ACS) and first-time DWI offenders (Form 90-AF). The Form 90 measures produce detailed quantity and frequency measure of alcohol use for the first-time offender that are validated by the CFM reports. Family functioning will be assessed at baseline, 3-month follow-up, and 9-month follow-up, as potential mediators of *B-SMART* effects, with DWI offenders and CFMs with three measures: (1) Family Environment Scale – Cohesion and Conflict subscales assesses offender and CFM perceptions of positive and negative family functioning; the two subscales selected are strongly associated with treatment outcome; (2) Family Communication Scale from FACES-IV assesses perception of quality of communication in the family; (3) Pleasant Events Schedule (adapted) assesses shared positive activities within a family. These three measures are also being used in the B-FIT study, allowing for comparison of outcomes across the two studies.

**3C.7.3. Ancillary Measures.** CASAA Demographics Form: This form collects participant identification data and demographic information (e.g., age, education, sex, and ethnicity) about DWI offenders and CFMs. Items will be added to describe the relationship between the offender and CFM and the frequency of contact between them. System Usability Scale: This scale consists of ten Likert strongly agree to disagree items (Cronbach's alpha=.90) that asks the respondent to rate the technology product being reviewed (Example items: I think that I would like to use this product frequently; I found the product very awkward to use; I felt very confident using the product). Participants also provide a final overall rating of the product along a 7-point worst imaginable to best imaginable dimension.

**3C.7.4. Server-side Process Measures of Mobile Web App Performance and Use.** KB's programmers will create custom programs to track the implementation and use of the *B-SMART mobile web app*, as we have done for other technology-based and mobile interventions). The mobile web app will be hosted on KB's secure web server. Users will register and use a password to access the *B-SMART mobile web app* and this password will be used to track use, keeping data about users private. KB utilizes Microsoft SQL server for data collection of users; click-stream (pages visited), time on *B-SMART*, and number of individual visits.

## 3C.8. Outcome Analysis Plan

The trial is intended to evaluate the following hypotheses:

**H1:** First-time DWI offenders in the intervention group (*B-SMART mobile web app*) will have significantly fewer IID lockout events than participants in the control group (UC information condition).

**H2:** Lower rates of IID lockout events will be mediated by improvements in Family Functioning, Family Communication, and Shared Positive Family Events in the intervention (*B-SMART mobile web app*) condition compared to the UC information condition.

We will also analyze moderation of the effect of *B-SMART* by demographics and mediation of IID lockout events by *B-SMART* use in the intervention group.

Three levels of analysis are planned: (1) hypothesis testing using Poisson regression testing the differences in lockout events between the two intervention groups, (2) analysis of possible covariates (e.g., sex, ethnicity, and age of DWI offenders and CFMs), added to the Poisson regression and (3) other exploratory analyses.

**3C.8.1. Preliminary Analysis of Baseline Data.** Descriptive data at baseline, with comparisons by treatment group, will be examined to check distributional characteristics and assess any concerns for imbalances that might be considered as covariates in analyses. The potential meaning of non-normality will be examined, i.e., excessive skewness potentially identifying key subgroups. These analyses will be at the level of the individual DWI offenders and CFMs responses and be conducted within 3 months of completion of recruitment. If there is excessive skewness on the IID lockout rates, negative binomial regression will be used.

**3C.8.2. Planned Analysis for Hypothesis 1.** The second major analysis will focus on impact of the *B-SMART mobile web app* on primary (IID lockout events) and secondary (DWI offender's alcohol consumption) outcomes, and be completed within 1 month of the end of the posttest data collection in Year 2. The effect of *B-SMART* on IID lockout events in Hypothesis 1 will be tested primarily using PROC GENMOD with a Poisson link via SAS Version 9.4, which includes capabilities to test these Poisson models with missing data, account for the temporal design, and include information by participant. Participants will be treated as a random effect and treatment as a fixed effect, at  $p=0.05$  (2-sided). Analyses of primary outcomes will not be released before completion of the intervention. Since CFM and DWI offender can be clustered within the same family, hierarchical models with participants nested within families will be considered.

The secondary outcome of quantity and frequency of alcohol consumption by DWI offenders will be compared in several ways. Quantity and frequency will be evaluated using Poisson models, as well as a composite variable based on total alcohol consumption (the product of the two variables), using negative binomial regression models, unless a Poisson model is sufficient.

Since date of IID lockout events will be collected and alcohol consumption is measured at all three assessments, we will examine the time by treatment interaction in the analyses of Hypothesis 1 to assess the question of the durability of the effects of *B-SMART* over time. For example, we will evaluate time to first lockout using a Kaplan Meier approach and the times to subsequent lockouts.

**3C.8.3. Mediation Analysis for Hypothesis 2.** To address the predicted mediation effects of family function on improving the effect of the *B-SMART mobile web app* in Hypothesis 2, we will assess a formal effect on predicting fewer IID lockout events. Mediation will be tested by applying regression techniques from Judd and Kenny and elaborated by MacKinnon, with significance of mediation determined via interval estimation using bootstrapping. Ratio of indirect to total effects will estimate the proportion of the effect mediated. The primary mediational analysis will rely on temporal order of assessments by examining the effect of *B-SMART* on change in the mediators from baseline to 3-month follow-up and in turn their association with changes in the IID lockout events from baseline to the 9-month follow-up and from 3- to 9-month follow-up.

**3C.8.4. Ancillary Analysis of Moderators.** Potential moderators (see 3C.7.3) will be tested at  $p=.05$  (2-tailed) unadjusted for multiple tests. For Hypothesis 1, they will be added as interactions by condition in a manner similar to regression testing for effect modification. Gender is included to probe differences by sex of DWI offenders and CFMs. For Hypothesis 2, we will explore if improvements in IID lockout events produced by increases in family function by different participant groups (sex, ethnicity, age, etc.), using moderated mediational analyses. Moderation effects must be large to be detected, so these are ancillary tests.

**3C.8.5. Ancillary Analysis of the *B-SMART Mobile Web App* Exposure.** The same mediational analysis techniques described in 3C.8.4 will be used to explore the relationship of exposure to the *B-SMART mobile web app* and pre-post changes in IID lockout events. Summed scores on exposure will be calculated from the SQL database (e.g., time on app, number of visits to the app, etc.) to assess intervention exposure.

### 3C.9. Strengths and Limitations to Approach

The research has several strengths. A scientifically-rigorous pretest-posttest randomized controlled design is used. Randomization will equalize participants across conditions. Established recruitment protocols and measures will be used and IID lockout events will be measured from court records, an objective assessment. The *B-SMART mobile web app* is built on our B-FIT theory- and evidence-based family intervention. Data collection will be automated (i.e., court records and online survey) so project staff are blind to condition. We minimized potential problems. Participation will be confidential to minimize selection bias. Valid, easy-to-administer, and low-cost self-report measures of mediators will be used to control social desirability biases and any bias is equalized by randomization.

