Orientation to *B-SMART* will be primarily self-explanatory, which we will confirm in usability testing (see 3C.5.6). In our past research, nearly all adults were adept at using a web browser across devices, so we are confident that *B-SMART* and its use will take little explanation. To ensure use, we will: 1) design the mobile web app to be inherently interesting and enjoyable through our iterative development procedures incorporating user input (see C3.5.2); 2) make the user navigation simple and easy to browse so modules can be viewed quickly; 3) create a mobile web app that can be completed in no more than 120 minutes to avoid boredom that provokes drop out; 4) program the mobile web app so its interface is optimized on a variety of technology platforms (smartphone, tablet computer, or personal computer) to accommodate the preferences of any user; and 5) engineer low and high bandwidth versions of the mobile web app that automatically adjust to the user's bandwidth access. While connectivity data in 3C.5.5 indicates sufficient broadband and cell coverage in New Mexico for the *B-SMART mobile web app*, this programming feature will allow the use of *B-SMART* even in limited connectivity situations. Reminders to use *B-SMART* (or read the IID Information pamphlet in UC group, see 3C.6.3) will be sent to participants every 5 days for two weeks after randomization. If the either the mobile web app (or the web pamphlet in the UC group) still is not accessed, research staff will contact participants by telephone and encourage them to use it.

**3C.6.4. Usual and Customary IID Information.** Participants randomized to the usual and customary care (UC) group will receive a website with a pamphlet on the IID installed in their vehicle and the manufacturer information provided about the IID in PDF format, in both English and Spanish. This constitutes a UC group, as such pamphlets are widely distributed to DWI offenders who have IIDs installed in their vehicles. Thus, providing this pamphlet represents a standard information provision for first-time DWI offenders and their CFMs.

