**3C.6.5. Sample Size Determination.** The sample size for the randomized trial in the Phase II research is designed to provide sufficient information for Phase III commercialization. The sample size assumes the counts of interlocks are Poisson distributed. We have assumed 4 interlocks over 9 months in the control arm or a rate of 0.44 per month for each DWI offender. In the *B-SMART mobile web app* group, we have assumed a reduction of 40% from 0.44, resulting in a rate of 0.27 per month. The null hypothesis is that the ratio of these two rates is 1.0 versus 0.6. Assuming a Type I error of 0.05 (2-sided), 90% power, sample size is only 27 DWI offenders per group. However, if the rate is higher up to 1 per month, the sample size required declines since the percent reductions yield wider absolute differences in the rates. We also are keen to know the reductions achievable with the *B-SMART* group, so we evaluated the sample size with regards to other effect sizes. A Cochrane meta-analysis reported the impact of IIDs to reduce risk by 64%, but with a confidence interval that ranged from 76% to 37%. In the proposed trial, we have two treatment groups and may see less impact than that in the meta-analysis. Thus, a sample size of 119 DWI offenders per group will allow for 90% power with a comparison of 0.44 to 0.36 or approximately a 20% reduction in interlocks. We will adjust for an expected 15% attrition and this sample size also has sufficient sample size to evaluate the impact in various gender and ethnic subgroups. Thus, we propose to randomize 150 DWI offenders and 150 CFMs to each arm of the trial.

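### Randomisation does not equalise arm-related reporting bias in the self-reported mediators, so the H2 indirect effect can reach significance with no true change in family functioning

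*Combined protocol and SAP*

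**What the plan says.** Section 3C.9 lists among the design's strengths that "self-report measures of mediators will be used to control social desirability biases and any bias is equalized by randomization". This sentence is not repeated in the SAP.

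The mediators (section 3C.7.2) are the Family Environment Scale cohesion and conflict subscales, the Family Communication Scale and an adapted Pleasant Events Schedule. All are completed by offender and CFM. Section 3C.8.3, the analysis plan under item 4.4 of the clinical trials form, and the SAP describe the same H2 test. The arm effect on mediator change from baseline to 3 months is linked to the association of that change with lockouts. Significance is judged by a bootstrap interval, and the ratio of indirect to total effect is reported.

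On blinding, section 3C.9 says that data collection is automated, "so project staff are blind to condition". Section 3C.6.3 says that if the app or the control pamphlet is not opened, "research staff will contact participants by telephone and encourage them to use it".

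**The concern.** A general tendency to give flattering answers is a baseline trait, and randomisation balances it in expectation. A change in reporting caused by the assigned arm arises after allocation, and randomisation cannot balance it. The mediators are scored after allocation.

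The design makes such a change plausible. Two of the four app modules (section 3C.5.1) cover shared positive activities and effective communication, which two of the mediator scales rate. Offender and CFM are randomised together, and the CFM is the app's primary user (section 3C.3), so the CFM rating is not an independent check. The control is a website with a device pamphlet (section 3C.6.4), no sham app is described, and the consent form states the project's purpose. The documents describe no social-desirability scale, no objective measure of the mediators and no H2 sensitivity analysis for reporting.

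H2 is one of two stated hypotheses and carries the claim that the app works through the family. A false indirect effect would credit family functioning with a benefit that it did not produce.

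**Working it through.** **1. The plan's own figures.** The mediation claim has no figure attached, so I first reproduced the sample size, which sets the n used below. Inputs from section 3C.6.5: "We have assumed 4 interlocks over 9 months in the control arm or a rate of 0.44 per month for each DWI offender"; "Assuming a Type I error of 0.05 (2-sided), 90% power, sample size is only 27 DWI offenders per group" for a rate ratio of 0.6; "a sample size of 119 DWI offenders per group will allow for 90% power with a comparison of 0.44 to 0.36", described as about a 20% reduction; and "We will adjust for an expected 15% attrition".

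Formula: n per group = (1.960 + 1.282)² × (1/m1 + 1/m2) / [ln(m2/m1)]², where m is the expected 9-month count.
- 4 vs 2.4: 10.51 × 0.6667 / 0.2609 = 26.8, so 27. Reproduced.
- 4 vs 3.2: 10.51 × 0.5625 / 0.04979 = 118.7, so 119. Reproduced.
- 119/0.85 = 140, below the planned 150. Retained: 300 × 0.85 = 255, or 127.5 per arm.

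**2. What a one-arm reporting shift does.** Let a be the arm effect on the mediator and b the mediator coefficient for lockouts, adjusted for arm. Adding a constant d to app-arm scores raises a by d. It leaves b unchanged, because the arm term absorbs the constant. The indirect effect moves by d × b, the direct effect by −d × b, and the total effect does not move. The shift alone is therefore not enough: b must also be non-zero.

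**3. How readily path a becomes significant.** Assumptions (not in the documents): observed SD 1, reliability 0.8, true baseline-to-3-month correlation ρ of 0.6 or 0.8. The SD of the observed change is √[2(1 − 0.8ρ)], which is 1.02 or 0.85. Its standard error is SD × √(2/127.5), which is 0.128 or 0.106. Shifts of 0.2, 0.3 and 0.4 SD give z of 1.6, 2.3 and 3.1 (ρ = 0.6) or 1.9, 2.8 and 3.8 (ρ = 0.8).

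**4. How strong path b is.** Assume that true 3-month function correlates r = −0.2 to −0.3 with lockout propensity, and that baseline function relates to propensity only through it. In absolute value, the observed mediator's correlation with propensity is:
- 3-month level: r√0.8 = 0.18 to 0.27.
- Raw change: r√0.8(1 − ρ)/SD of change = 0.07 to 0.11 (ρ = 0.6) or 0.04 to 0.06 (ρ = 0.8). It is zero if true function is stable (ρ = 1).
- 3-month score adjusted for baseline: r√0.8(1 − 0.8ρ²)/√(1 − 0.64ρ²) = 0.15 to 0.22 (ρ = 0.6) or 0.11 to 0.17 (ρ = 0.8).

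The choice of mediator score therefore drives the result.

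**5. Simulated false significance of the indirect effect.** 255 offenders, no true effect on the mediator, the assumptions above, shifts 0.2 to 0.4 SD.

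| Mediator score | False significance |
|---|---|
| Raw change (section 3C.8.3) | 3% to 21% |
| 3-month score adjusted for baseline | 14% to 75% |
| 3-month level only | 15% to 82% |
| No shift | 0% to 2% |

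A separate run (400 trials per setting, lockout log-SD 0.8) splits the raw change score by shift of 0.2, 0.3 and 0.4 SD: 3–7%, 10–18% and 14–22% at ρ = 0.6; 2–5%, 5–9% and 7–13% at ρ = 0.8; and 1–4% throughout if true function is stable. In a further simulation with a single mediator score, a shift without any within-arm association gave 0% to 4%.

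**6. If the app works by another route.** Take a true 20% cut in lockouts that does not pass through the mediator, and a single mediator score with no baseline. With a rate ratio of 0.9 per SD of true function and a 0.5 SD shift, the false indirect effect is 0.5 × √0.8 × ln 0.9 = −0.047. The total is ln 0.8 = −0.223, so the false proportion mediated is 0.047/0.223 = 21%. Raw change scores weaken b and so reduce this share.

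**The case against.** The strongest objection concerns size. Section 3C.8.3 analyses change, and a change score removes most of the stable differences between families that would link the mediator to lockouts. A reader might infer that false support in most trials is to be expected under the written plan. The documents do not support that: such rates need a 3-month level or a baseline-adjusted model, and section 3C.8.3 states neither. This part stands. What remains is a smaller inflation, plus exposure to the larger one if analysts adjust for baseline.

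Nor do the documents show that the within-arm association exists. They say only that two subscales are related to treatment outcome. The association and the shift sizes are assumptions.

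H2 also presupposes fewer lockouts in the app arm. When the app has no effect on lockouts, a significant indirect effect together with a significant lockout reduction occurred in only 0% to 3% of simulated trials. This stands too, and limits the main risk to an app that works by another route.

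Participants' knowledge of their arm is an inference from the design. The tick marks under item 4.2.f are not readable, and nothing is concluded from them. Confidential online completion may lower social desirability overall, but it does not remove a difference between arms.

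Finally, the staff-blinding sentence is tied to automated data collection. Its wording is too broad, but it has no bearing on how families report.

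**Conclusion.** The statement that randomisation equalises the bias is wrong for mediators rated after allocation, and nothing else in the documents guards H2 against reporting that differs by arm. For assumed shifts of 0.2 to 0.4 SD, false significance of the indirect effect is about 3% to 21% with the planned change score and about 14% to 75% with baseline adjustment, against 0% to 2% with no shift. These figures rest on assumed reliability (0.8), stability (0.6 to 0.8) and mediator-lockout correlation (−0.2 to −0.3). The direction is firm and the size is not: H2 can be falsely supported, not that it will be.

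A reader might extend the point to H1. The documents do not support that, because lockouts come from program records and not from participants' reports.

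**What to change.** 1. In section 3C.9, delete the claim that randomisation equalises the bias.
2. In the H2 analysis (section 3C.8.3, item 4.4 of the form, and the SAP), add a tipping-point analysis. Subtract an assumed reporting shift of 0 to 0.4 SD from app-arm follow-up mediator scores, for offender and for CFM reports, and report the shift at which the indirect effect loses significance. Run it under whichever mediator score is fitted. With arm in the lockout model, b does not change, so only path a has to be shifted.
3. Word the H2 conclusion in the light of that tipping point.
4. Minor wording: limit the staff-blinding statement to record extraction and survey data collection, since research staff telephone participants about their assigned app or pamphlet.

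Comparing Form 90 drinking with lockouts or CFM reports should not be offered as a remedy. It tests reporting of drinking, not of cohesion, communication or shared activities.

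The cost is a few lines of text, a small sensitivity analysis on data already planned, and a more guarded H2 conclusion.

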## PHS Human Subjects and Clinical Trials Information

OMB Number: 0925-0001 and 0925-0002

Expiration Date: 03/31/2020

Are Human Subjects Involved

Yes  No

Is the Project Exempt from Federal regulations?

Yes  No

Exemption Number

1  2  3  4  5  6  7  8

Other Requested Information

**Human Subject Studies**

Study#	Study Title	Clinical Trial?
1	B-SMART: A randomized trial of a smartphone app for DWI Offenders and their Families	Yes

## Section 1 - Basic Information (Study 1)

OMB Number: 0925-0001 and 0925-0002

Expiration Date: 03/31/2020

### 1.1. Study Title \*

B-SMART: A randomized trial of a smartphone app for DWI Offenders and their Families

### 1.2. Is this study exempt from Federal Regulations \*

Yes  No

### 1.3. Exemption Number

1  2  3  4  5  6  7  8

### 1.4. Clinical Trial Questionnaire \*

1.4.a. Does the study involve human participants?

Yes  No

1.4.b. Are the participants prospectively assigned to an intervention?

Yes  No

1.4.c. Is the study designed to evaluate the effect of the intervention on the participants?

Yes  No

1.4.d. Is the effect that will be evaluated a health-related biomedical or behavioral outcome?

Yes  No

### 1.5. Provide the ClinicalTrials.gov Identifier (e.g.

NCT87654321) for this trial, if applicable

